#### **The study has 4 parts to it;**

#### **Healthy human subjects;**

Healthy human subjects ranging in age between 18 to 80 years and who are able to give informed consent are considered candidates for study. Pregnant subjects and those taking medications known to affect gastrointestinal motility are excluded from study.

Approximately 30 healthy volunteers will be recruited for this next phase of the study. All previously enrolled healthy volunteers in the earlier phase of the study (IRB# 1206008988) can also enroll in this phase of the study. The study team may reach out to them to see if they would like to receive more information about this new phase of the study. If they are willing, then information will be provided to them and if they are interested then they will be contacted for a screening visit. The team feels that by reaching out to the previously enrolled subjects with the possibility of repeating some parts of the study as dictated by the protocol, they would be able to verify the previous results and thus help in the research.

If the previously enrolled subjects are not reachable or not interested, then new healthy volunteers will be enrolled.

#### Inclusion Criteria

- Healthy volunteers with no gastric symptoms or conditions (except due to COVID 19)
- Aged 18-80 years
- Willing to have electrodes placed in the external ear (ABVN arm)
- Willing to perform vagal activity maneuver (Vagal arm)
- Willing to have 1 tablespoon (15 ml) of blood drawn at 3 time points

#### Inclusion criteria for VNS Therapy subjects

1. Volunteers with no GI symptoms
2. Ages 18-80
3. Undergoing VNS Therapy as part of clinical treatment for focal or partial epilepsy or seizure
4. Willing to have MEA electrodes placed on the neck and bipolar electrodes placed on chest and stomach

#### Exclusion Criteria

- Unable to provide consent
- Having gastric motility issues (not due to COVID 19) as determined by the PI or Sub I
- Taking medications affecting gastric motility
- Pregnant females
- Prisoners

#### **Study Procedures:**

Healthy volunteers who meet the inclusion and exclusion criteria will be enrolled in the study. They will complete a Health History questionnaire that asks in detail about their health history along with any medications that they may be on. If they have been diagnosed with COVID 19 then they will be asked to complete another questionnaire about their symptoms. If they meet all the requirements for the study, then they will do the following

#### **EAR STIMULATION GROUP:**

This is a onetime visit only that involves baseline and test procedures.

1. Two MRI compatible electrodes will be placed in the auricle of the left ear, fixed by a plastic armature that wraps around the ear. The leads from the electrodes are connected to a stimulator.
2. A pneumatic belt may be placed around the lower thorax. Pneumatic tubes connect this belt to a pressure transducer that in turn sends signal to a laptop-controlled device that acquires the signals.

3. Two ECG electrodes are placed on both sides of the neck overlying the area near the carotid artery where the vagus nerve is superficial. This is to measure the vagal action potentials in the neck.
4. Two ECG electrodes are placed one on each arm and one on the chest for measurement of the electrocardiogram (ECG)
5. Three ECG electrodes are placed on the abdomen in a line parallel to the longitudinal axis of the stomach to record the electrogastrogram (EGG).

Electrical stimulation of the electrodes placed in the ear is provided by a current-constant stimulator. The stimuli consist of rectangular pulses with  $450\text{ }\mu\text{s}$  pulse width, delivered at 30 Hz, and pulse train duration of 0.5 seconds. Stimulation is gated, with 0.5-second delay, after peak inhalation (i.e., during exhalation) or after peak exhalation (i.e., during inhalation).

Baseline procedure:

A butterfly catheter is inserted under aseptic conditions into a peripheral vein. Fifteen ml (1 tablespoon) of blood is withdrawn and placed on ice. After this the baseline recording will be started as described below.

During the baseline recording the stimulating electrodes are placed in the auricle of the subject but no current is delivered. Cervical neck electrodes are placed over the right and left vagus nerve to record any electrical activity that might occur during the baseline period. Baseline ECG and EGG recordings are also performed during this interval.

Test procedure:

Stimuli consisting of rectangular pulses with  $450\text{ }\mu\text{s}$  pulse width, delivered at 30 Hz, and pulse train duration of 0.5 seconds are then delivered to the subject. Current intensity is set to achieve moderate to strong (but not painful) sensation, and pulse frequency/duration is set following pilot testing to achieve a subjectively comfortable stimulus sensation. Starting current is 0.1mA and the maximum current that can be given will not exceed 5.0 mA. This is 4 out of 10 and is designated “100 per cent.” The current amplitude is then increased again by 10 per cent and ABVN is applied again for 60 seconds. This sequence is repeated until the “100 percent” level (4/10) is reached. Based on the previous study we find that the target of 4/10 may correlate with a current of somewhere between 1.0 and 3.5 mA, but this is variable from subject to subject.

Sensation of 10/10 may correlate with close to 10.0 mA. The time that may elapse from the start to reaching the 100% target is very variable and may range from 5 minutes to 15 minutes. It depends upon how soon the subject reaches the subjective 4/10 sensation. These stimuli are delivered during expiratory phase of respiration as investigations have shown this to be most effective in producing vagal stimulation (8).

Once the target stimulus intensity has been achieved, stimuli are delivered during the expiratory phase for a total of two minutes. Another 15 ml (1 tablespoon) of blood will be collected 20 minutes after stopping the stimulus.

The subject will be allowed to keep on resting and 20 minutes after the second blood draw, another 15 ml (1 tablespoon) of blood will be drawn. This is the final draw. The catheter will then be withdrawn, and the subject will be allowed to go home

ECG and EGG recordings are continued during auricular branch vagal nerve stimulation.

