### **Technique of transcutaneous auricular vagus nerve stimulation**

Two electrodes are placed in the auricle of the left ear at loci described by the (1) the cyma concha and (2) the slope between the antihelix and cavum concha (Figs. A and B).

These locations are chosen based on auricular sub regions with the greatest probability of vagal innervation of the human auricle, as has been previously determined by cadaver dissection (9) Electrodes are passed through the penetration panel with inline low-pass radio frequency filtering (80 MHz). Electrical stimulation to these electrodes is provided by a constant-current stimulator with 100 V compliance (FE 180 Stimulus Isolator, AD Instruments, Boston MA).

Stimuli consist of rectangular pulses with 450  $\mu$ s pulse width, delivered at 30 Hz, and pulse train duration of 0.5 seconds, as previously described in studies of chronic pain patients (10). Stimulation is gated, with 0.5-second delay, after peak inhalation (i.e., during exhalation) or after peak exhalation (i.e., during inhalation).

Respiratory gating for stimulation requires real-time evaluation of the respiratory cycle. We use a respiratory belt transducer designed to measure changes in chest diameter resulting from breathing (Fig. C). This pneumatic belt is placed around the subject's lower thorax at the level of maximum respiratory expansion (TN 1132/ST Respiratory Belt, AD Instruments, Boston MA). The belt is pretensioned slightly. The belt contains a capacitive sensing element and custom electronics that respond linearly to changes in length. The transducer is connected to a PowerLab pod port (Power Lab, AD Instruments, Boston MA). The transducer contains a flexible sensing element bonded to the inside of the fabric belt.

Once electrode placement in the ear is validated, subjects are asked to rate stimulation intensity of 0 to 10 (0: no sensation, 10: mild discomfort). Current intensity is set to achieve moderate to strong (but not painful) sensation (target score: 4/10), and this current intensity is used on subsequent stimulation runs. For SHAM baseline study, the electrode in the ear remains in place, but the leads are disconnected from the stimulator.

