#### ABVN Phase 2 Outcome Measures/Endpoints

1. To measure the amplitude of vagal nerve compound action potentials in gastroparetic subjects with symptoms of nausea and vomiting with skin electrodes over right and left vagus nerve during ABVN stimulation and also during the vagal maneuvers phase
2. To measure respiratory changes in heart rate during ABVN and also during the vagal maneuvers phase.
3. To measure changes in the amplitude of the surface electrogastrogram during ABVN and also during the vagal maneuvers phase.
4. To measure the Heart rate variability(HRV), vagal nerve compound action potentials and electrogastrogram in subjects undergoing VNS Therapy for focal or partial seizures.
5. To measure the effect of ABVN stimulation on the gastric hormones in healthy and gastroparetic subjects.
6. To see the effect on the data if we change the regular ECG electrodes to MEA electrodes in the neck.
7. To see the effect of COVID 19 on HRV in healthy volunteers diagnosed with COVID-19

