#### **VAGAL MANEUVER GROUP:**

Healthy volunteers will be recruited initially to see the effect of these maneuvers on the vagal activity.

A total of 10 healthy volunteers will be recruited. These subjects can be the same subjects that enroll in the ear stimulation group of the study or can be entirely new subjects.

At the beginning of the study, a baseline recording of 10- 20 minutes will be made following which the maneuvers will be conducted. Cervical neck electrodes used in this part of the study will include the multi electrode array (MEA) that are currently being used for a different protocol (IRB 1907095542). The MEA can be placed on either side of the neck over the area of the vagus nerve to record any electrical activity that might occur during the baseline period. Baseline ECG and EGG recordings are also performed during this interval by placing the electrodes over the chest and over the stomach area for ECG and EGG recordings.

In a previous protocol (IRB 1809685671) healthy volunteers have already been recruited using the bipolar ECG electrodes for the vagal nerve recording in the neck, hence a total of 10 healthy volunteers to be recruited using the MEA electrodes for comparison of data.

After 10 seconds of each maneuver, another 10-20 minutes of recording will be made before doing the next maneuver.

For the eating maneuver, there is no time restriction and the subject will drink it as per their capacity.

We will include the following maneuvers:

Cough; Each subject will be asked to generate approximately 6 to 8 forceful and sustained coughs for 10 seconds.

Cold stimulus to face: We propose to place a washcloth soaked in ice water on each subject's face for about 10 seconds. This creates a physiological response to a person being submerged in cold water (Diver's Reflex)

**Carotid Massage:** This technique is performed with the subject's neck in an extended position, the head turned away from the side being massaged. Only one side is massaged at a time. Pressure is applied underneath the angle of the jaw in a gentle circular motion for about 10 seconds. The subject is monitored throughout.

**Gagging:** A tongue depressor is briefly inserted into the subject's mouth for about 10 seconds touching the back of the throat, which causes the person to reflexively gag. The gag reflex stimulates the vagus nerve.

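### The first hormone sample is drawn before the no-current recording, so the pre-to-post hormone change includes the sham period and any response to venipuncture

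*Protocol*

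**What the plan says.** The Protocol's outcome list (ABVN Phase 2 Outcome Measures/Endpoints, item 5) includes: "To measure the effect of ABVN stimulation on the gastric hormones in healthy and gastroparetic subjects".

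The Ear Stimulation Group sections for healthy and for gastroparetic subjects give the same order of events:

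- The baseline procedure opens with the catheter: "A butterfly catheter is inserted under aseptic conditions into a peripheral vein".
- The first sample follows at once: "Fifteen ml (1 tablespoon) of blood is withdrawn and placed on ice. After this the baseline recording will be started as described below".
- That recording is the no-current period: "During the baseline recording the stimulating electrodes are placed in the auricle of the subject but no current is delivered". The section on stimulation technique describes the sham in the same way: "For SHAM baseline study, the electrode in the ear remains in place, but the leads are disconnected from the stimulator".
- Current is then raised stepwise to the target sensation. For healthy subjects the time this takes "may range from 5 minutes to 15 minutes".
- Stimulation at target lasts two minutes, and then: "Another 15 ml (1 tablespoon) of blood will be collected 20 minutes after stopping the stimulus".
- A third sample is taken 20 minutes after the second.

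The Data Analysis section compares CNAP amplitude with the sham baseline. For hormones it says only which team will process and analyse the samples.

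**The concern.** For the recorded signals (CNAP, ECG, EGG), the no-current period is the baseline that stimulation follows. For hormones, the same period lies after the baseline sample, inside the interval over which change is measured. Any movement in hormone levels during the sham recording, and any response to the needle, is then counted in the change from sample 1 to sample 2.

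The ear-stimulation sections state no fasting condition; overnight fasting appears only for the eating maneuver. Drift over the session therefore cannot simply be assumed to be negligible.

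One listed endpoint is affected, in about 30 healthy and about 40 gastroparetic subjects. The sampling schedule is fixed in the protocol, so a statistical analysis plan could choose the contrast but could not recover a sample that was never drawn at the end of sham.

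**Working it through.** The protocol gives no figure for this interval, so there is nothing to reproduce. The check is timeline arithmetic.

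**Inputs**

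- b, the no-current recording: not stated for the ear-stimulation sessions. The maneuver sessions state: "At the beginning of the study, a baseline recording of 10- 20 minutes will be made following which the maneuvers will be conducted". I assume b = 10–20 min and also show 0 and 30 min.
- t, titration to target: 5–15 min (Ear Stimulation Group, healthy subjects only; no time is given for gastroparetic subjects).
- Stimulation at target: 2 min.
- Wait before sample 2: 20 min.

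**Formulas**

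- Sample 1 to sample 2 = b + t + 2 + 20.
- Stimulation of any kind = t + 2, counting the whole titration as stimulation.

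| b (min) | t (min) | Sample 1 to 2 (min) | Any stimulation (min) | Share |
|---|---|---|---|---|
| 0 | 5 | 27 | 7 | 25.9% |
| 0 | 15 | 37 | 17 | 45.9% |
| 10 | 5 | 37 | 7 | 18.9% |
| 10 | 15 | 47 | 17 | 36.2% |
| 20 | 5 | 47 | 7 | 14.9% |
| 20 | 15 | 57 | 17 | 29.8% |
| 30 | 5 | 57 | 7 | 12.3% |
| 30 | 15 | 67 | 17 | 25.4% |

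Under the assumed 10–20 min, the interval is 37–57 min, with 7–17 min of stimulation.

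**If sample 1 is taken at the end of the no-current recording**, b drops out: 5 + 2 + 20 = 27 min to 15 + 2 + 20 = 37 min, plus any settling time added. The part removed is b/(b + t + 22). It is smallest at b = 10, t = 15 (10/47 = 21%) and largest at b = 20, t = 5 (20/47 = 43%).

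**Between-subject spread.** The stated titration range gives a spread of up to 15 − 5 = 10 min in healthy subjects. Moving the sample does not change this.

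**The case against.** Several objections stand and limit the point.

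- **Attribution.** A reader might infer that the draw order is why the hormone change cannot be attributed to stimulation. The documents do not support that. Titration is itself stimulation, and the 20-minute wait is a planned sampling lag that stays under any order. The order adds only the sham period and the time just after venipuncture. The larger obstacle is that there is no hormone series without stimulation, and moving one sample does not supply it.
- **Exposure.** Counting only the two minutes at target would understate exposure, because current is also delivered during titration.
- **Third sample.** It is tempting to read sample 3 minus sample 2 as a check on drift. Both samples follow stimulation, at 20 and 40 minutes after it stops, so the difference mixes drift with a fading response.
- **Elapsed time.** After re-ordering, elapsed time varies mainly with titration time, which is also stimulation received. Adjusting for it may adjust away exposure.
- **Size of bias.** The figures are minutes, not bias. Nothing in the protocol shows that these hormones move over 10–20 minutes or respond to a needle. If the sham is very short, the gain is small.
- **Signal comparison.** The present order keeps blood sampling away from the change from sham to stimulation, where CNAP amplitudes are compared. A draw placed there is a real though small downside, which a short settling period limits.

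None of this gives a hormone reason for placing the baseline sample ahead of the sham recording.

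**Conclusion.** The point holds in limited form. In both cohorts the baseline hormone sample precedes the no-current recording, so the sample 1 to sample 2 change includes the sham period and any venipuncture response. This follows from the stated sequence, whatever the length of the sham.

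The size depends on two things: a sham length of 10–20 minutes borrowed from the maneuver sessions, and titration times stated for healthy subjects only. On that basis the interval is 37–57 minutes, and 10–20 minutes of it (21–43%) is avoidable. For gastroparetic subjects the order is the same, but the interval cannot be computed from the protocol. The direction and amount of any bias are unknown.

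The change is worth making before further samples are collected, because it is cheap and cannot be made afterwards. It improves the baseline; it does not turn a single-arm pre-post comparison into a controlled one.

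**What to change.** In both Ear Stimulation Group sections:

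1. Insert the catheter, run the no-current recording, then take sample 1 through the indwelling catheter just before the first current.
2. Allow a short settling period between that draw and the start of stimulation, so that the CNAP, ECG and EGG comparison is not disturbed.
3. State the length of the no-current recording, and record clock times for all three draws and for stimulation start and stop.
4. Describe the hormone result as an uncontrolled pre-post change. Attribution to stimulation would need no-stimulation samples at matching times, from a sham session or sham group.
5. Do not use sample 3 minus sample 2 as a drift check. Use elapsed time as a sensitivity covariate at most.

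The Study Objectives section also speaks of hormones during stimulation, but no sample is scheduled then; the two should be reconciled in the same revision.

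**Cost:** items 1 to 3 use the same catheter, the same three draws and the same volume. They add the settling time and a brief draw between sham and stimulation. A no-stimulation series would be a larger change and is optional if item 4's description is adopted.

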#### **VAGAL MANEUVER GROUP:**

Healthy volunteers will be recruited initially to see the effect of these maneuvers on the vagal activity.

A total of 10 healthy volunteers will be recruited. These subjects can be the same subjects that enroll in the ear stimulation group of the study or can be entirely new subjects.

At the beginning of the study, a baseline recording of 10- 20 minutes will be made following which the maneuvers will be conducted. Cervical neck electrodes used in this part of the study will include the multi electrode array (MEA) that are currently being used for a different protocol (IRB 1907095542). The MEA can be placed on either side of the neck over the area of the vagus nerve to record any electrical activity that might occur during the baseline period. Baseline ECG and EGG recordings are also performed during this interval by placing the electrodes over the chest and over the stomach area for ECG and EGG recordings.

In a previous protocol (IRB 1809685671) healthy volunteers have already been recruited using the bipolar ECG electrodes for the vagal nerve recording in the neck, hence a total of 10 healthy volunteers to be recruited using the MEA electrodes for comparison of data.

After 10 seconds of each maneuver, another 10-20 minutes of recording will be made before doing the next maneuver.

For the eating maneuver, there is no time restriction and the subject will drink it as per their capacity.

We will include the following maneuvers:

Cough; Each subject will be asked to generate approximately 6 to 8 forceful and sustained coughs for 10 seconds.

Cold stimulus to face: We propose to place a washcloth soaked in ice water on each subject's face for about 10 seconds. This creates a physiological response to a person being submerged in cold water (Diver's Reflex)

**Carotid Massage:** This technique is performed with the subject's neck in an extended position, the head turned away from the side being massaged. Only one side is massaged at a time. Pressure is applied underneath the angle of the jaw in a gentle circular motion for about 10 seconds. The subject is monitored throughout.

**Gagging:** A tongue depressor is briefly inserted into the subject's mouth for about 10 seconds touching the back of the throat, which causes the person to reflexively gag. The gag reflex stimulates the vagus nerve.

**Valsalva maneuver:** The subject is instructed to bear down as if they were having a bowel movement. The subject is asked to blow through a mouthpiece that is hooked to a device used in clinical spirometry until the pressure reaches 10mmHg. Alternatively, we can have the subject blow through the barrel of a 10 ml syringe for 10 seconds. This maneuver increases intrathoracic pressure and stimulates the vagus nerve.

**Eating:** Subjects will be asked to drink water or/ and Ensure Original that has 220 calories after fasting overnight to see the effect on vagal activity during eating. The subjects take their time to drink the water or ensure and the time to finish the drink is noted.

All the maneuvers described above will be conducted for duration of 10 seconds each except wherever stated otherwise and the recordings will be made for duration of 5-10 minutes after each maneuver. If it is not possible to do all the maneuvers in one visit, then they will be conducted over two visits. Sometimes not all maneuvers will be conducted, and this will depend on the discretion of the investigator.

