Eating: Subjects will be asked to drink water or/ and Ensure Original that has 220 calories after fasting overnight to see that effect on vagal activity during eating. The subjects take their time to drink the water or ensure and the time to finish the drink is noted.

All the maneuvers described above will be conducted for duration of 10 seconds each except wherever stated otherwise and the recordings will be made for duration of 5-10 minutes after each maneuver. If it is not possible to do all the maneuvers in one visit, then

they will be conducted over two or more visits. Sometimes not all maneuvers will be conducted, and this will depend on the discretion of the investigator.

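### The visit at which gastric hormones are sampled sets no meal-state condition and mentions no record of last meal or clock time, so meal-related hormone change can be mistaken for a stimulation effect or add noise to it

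*Protocol*

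**What the plan says.** The outcome list (ABVN Phase 2 Outcome Measures/Endpoints, item 5) includes this aim: "To measure the effect of ABVN stimulation on the gastric hormones in healthy and gastroparetic subjects". The blood for it comes from the ear-stimulation visit, described in near-identical terms for healthy volunteers and for gastroparetic subjects without stimulators: "This is a onetime visit only that involves baseline and test procedures".

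The sequence at that visit is as follows.

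- **First sample:** "Fifteen ml (1 tablespoon) of blood is withdrawn and placed on ice. After this the baseline recording will be started as described below". The sham (no-current) baseline recording therefore follows the first sample.
- **Titration:** in the healthy-volunteer section, the time to reach the target sensation "may range from 5 minutes to 15 minutes". The gastroparetic section gives no titration time.
- **Stimulation:** at target, "stimuli are delivered during the expiratory phase for a total of two minutes".
- **Second sample:** it "will be collected 20 minutes after stopping the stimulus".
- **Third sample:** 20 minutes after the second, with the subject resting.

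Neither ear-stimulation section, nor the eligibility criteria of either cohort, mentions fasting, a standard meal, time of last meal or time of day.

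Meal state is controlled elsewhere. Under Vagal Maneuver Group, Eating, healthy volunteers take the drink "after fasting overnight to see the effect on vagal activity during eating", and gastroparetic subjects do so "after fasting overnight to see that effect on vagal activity during eating". In both cohorts the same people may take part in the maneuver and ear-stimulation groups.

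**The concern.** The protocol treats intake as something that acts on the vagus nerve: it makes drinking one of the vagal maneuvers and controls the preceding meal state for it. At the visit where gastric hormones are the outcome, meal state is neither fixed nor, as far as the text shows, recorded.

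The hormone effect is read as change within a subject over the visit. If a subject is still digesting, the level may move during that time whether or not current is delivered. Across subjects this adds variance. If the movement has a net direction, it looks like a stimulation effect. The Background section calls delayed gastric emptying characteristic of gastroparesis, so the same interval since the last meal can leave the two cohorts in different digestive states.

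This is a matter of visit conduct, not something normally left to an analysis plan. A statistician cannot adjust later for a time that was not collected.

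**Working it through.** The protocol states no effect size, variance or power for the hormones, so there is no figure of its own to reproduce. The check has three steps.

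**1. Interval over which change is read (healthy volunteers).** Let L be the length of the baseline recording, which is not stated for this visit.

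- First to second sample: L + titration (5 to 15) + stimulation (2) + wait (20) = L + 27 to L + 37 min.
- First to third sample: add 20 = L + 47 to L + 57 min.

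If L were 10 to 20 min (an assumption, borrowed from the vagal maneuver group), these become 37 to 57 min and 57 to 77 min. For gastroparetic subjects only 2 + 20 = 22 min and 22 + 20 = 42 min can be summed, plus titration and baseline recording of unstated length.

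**2. What three samples can separate.** Write s for the stimulation effect and m for the meal-related change since the first sample.

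- Second minus first = s2 + m2.
- Third minus first = s3 + m3.

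There are two observed changes and four unknowns. The first sample precedes the sham recording and both later samples follow stimulation, so no change is a pure m. The third sample helps under added assumptions. If the drift is a straight line and the stimulation effect has gone by the third sample, then s2 = (second minus first) − (T2/T3) × (third minus first), where T2 and T3 are the elapsed times. With L left out, T2/T3 is 27/47 = 0.57 to 37/57 = 0.65. The protocol states neither assumption. A post-meal rise and fall could pass for response and recovery, and a steady slope could pass for a lasting effect.

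**3. Illustration of consequence.** The drift sizes below are assumptions; the document gives none. Suppose stimulation has no effect and the mean meal-related drift is d standard deviations of the change score. A two-sided 5% paired t test then rejects with the probability given by a noncentral t with noncentrality d√n.

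| d | n = 30: noncentrality, rejection | n = 40: noncentrality, rejection |
|---|---|---|
| 0 | 0, 5% | 0, 5% |
| 0.1 | 0.55, 8% | 0.63, 10% |
| 0.25 | 1.37, 26% | 1.58, 34% |
| 0.5 | 2.74, 75% | 3.16, 87% |

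Here 30 and 40 are the planned healthy and gastroparetic numbers. If the cohorts were compared and their drifts differed by d, the noncentrality is d/√(1/30 + 1/40) = 4.14d. A difference of 0.25 gives 1.04 and about 18% rejection; 0.5 gives 2.07 and about 53%. If meal timing produced no net drift (d = 0), the test keeps its 5% level and the cost is extra variance only.

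**The case against.** **No contradiction.** In the eating maneuver the drink is the stimulus, so fasting belongs to that procedure. A different preparation for a different visit is not an inconsistency. This stands: the point is a control left open at the hormone visit. The eating text matters only because it shows that the protocol regards intake as relevant to vagal activity.

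**Sources not shown.** The blood-draw design is based on an earlier protocol, which is also referred to for recording details, and a prior healthy-volunteer protocol is listed as an appendix. A meal condition may be set there, and the health-history questionnaire is not reproduced. This also stands, so one can say only that this protocol carries no condition into the visit and mentions no recording.

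**Third sample.** It follows a period without stimulation and gives some information. A reader might infer that meal and stimulation effects are wholly inseparable. That is too strong, as step 2 of the working shows.

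**Other readings the text does not support.**

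- That some subjects will in fact be fed: nothing says so.
- That electrogastrogram results are exposed over the same long interval: that recording is described for the baseline period and during stimulation, not through the rest and sampling period.
- That a cohort comparison is biased: item 5 names both populations but states no test between them.
- That delayed emptying defines the patient cohort: the Background calls it characteristic, and the inclusion criteria list no emptying test.

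None of this supplies a meal condition or a recorded time at the hormone visit.

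**Conclusion.** The concern holds in limited form. As written, the hormone visit leaves meal state and time of day uncontrolled and, as far as the text shows, unrecorded in both cohorts. Change is read over 27 to 37 and 47 to 57 minutes plus an unstated baseline length in healthy volunteers, with no sham-only sample. Meal-related change can therefore inflate variance, can be mistaken for a stimulation effect, and can differ between cohorts.

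The size cannot be derived from the document. The hormones are not named and no drift or variance is given, so the rejection rates above show only how a range of assumed drifts would act. The conclusion rests on two conditions: that no earlier protocol already fixes meal state for this visit, and that the hormones measured respond to meals over about an hour. It is worth correcting because the information cannot be recovered afterwards.

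**What to change.** Reconcile the ear-stimulation procedures in both cohorts with the eating-maneuver text, so that one stated meal-state condition applies to every hormone visit. If an earlier protocol already sets one, carry it into this protocol. Which condition to apply, including how it is handled in diabetic subjects, is for the study physicians.

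Whatever condition is chosen, record time since last meal and clock time at the first sample, and use both in the hormone analysis.

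The cost is one visit instruction, two recorded items and minor scheduling. The change removes or adjusts for the meal component only. Without a sham blood series, a plain effect of time over the visit remains, and the report should say so.
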